Inclusion criteria: Female patients over the age of 18 scheduled for laparoscopic gynecological procedures of the uterus, fallopian tubes, and/or adnexa benign disease will be included in our study.

Exclusion criteria: Males, women under 18 years of age, women who are pregnant or have suspected or known malignant disease, or women who are immunocompromised will be excluded from our study. Patients with known or persistent abuse of medication, drugs, or alcohol. Patients with chronic pain for greater than 3months will also be excluded.

 Mount Sinai	Protocol Name:	The Role of Acupuncture in Post-Operative Pain Management in Gynecological Patients
	Principal Investigator:	[name]
	Primary Contact Name/Contact Info:	[name], [name]
	Date Revised:	6/19/2016
	Study Number:	1896888

(NOTE: You may not include members of vulnerable populations as subjects in your research unless you indicate this in your inclusion criteria.)

c) Number of Subjects: 100

A total of 100 patients will be recruited and there will be 50 in the study group and 50 in the control group. This was determined because we are looking for a difference in narcotic use of 1.5 tablets to be considered significant. Assuming a standard deviation of 2.4 (prior data) , we will need to study 47 experimental subjects and 47 control subjects to be able to reject the null hypothesis that the population means of the experimental and control groups are equal and discern a difference of 1.5, with probability (power) 0.8. The Type I error probability associated with this test of this null hypothesis is 0.05.

d) Study Timelines

The anticipated duration of the study is 12 months including recruitment and data analysis. Eligible patients will be offered enrollment in the study during their pre-operative assessment with [name], [name], or [name] typically occurring 1-3 weeks prior to surgery. Patients will then be followed throughout their hospital course. Follow up will occur at their post-operative visits 2 weeks after the procedure.

e) Endpoints

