SPSS will be used for the data analysis. A power analysis was performed using prior data of narcotic use in [name] post-operative gynecological patients. This data demonstrated the average number of narcotic tablets consumed at 24 hours is 3, with a standard deviation of 2.4. Overall we are aiming to achieve a decrease of 50% (or 1.5 tablets) for post-operative narcotic use at 24 hours. The number of patients required for such a difference is 47 experimental subjects and 47 control subjects. The Type I error probability associated with this test of this null hypothesis is 0.05. Further Data analysis will be performed using SPSS. The analysis of pain medication use and admission rate will be performed using student t-tests and regression analyses.

 Mount Sinai	Protocol Name:	The Role of Acupuncture in Post-Operative Pain Management in Gynecological Patients
	Principal Investigator:	[name]
	Primary Contact Name/Contact Info:	[name], [name]
	Date Revised:	6/19/2016
	Study Number:	1896888

i) Provisions to Monitor the Data to Ensure the Safety of Subjects

1. MSSM Principal Monitor: [name] (PI)

Academic Title: Director, Division of Gynecology

[contact]

Email: [contact]

2. The choice of principal monitor is appropriate to assess the risks to the participants because he is the lead attending in this study and the attending physician of all of the study participants. He has done a large amount of gynecology research and has ample experience in assessing the safety and well-being of the participants.

3. All adverse events including contact dermatitis will be assessed at the specified endpoints. In addition the efficacy of the acupuncture in reducing pain will be determined.

4. The data will be analyzed after 50 and 100 patients.

5. The study will be terminated if it is determined that there is a significant difference between the study groups in post-operative pain control or if there are multiple incidences of adverse events related to the study protocol.

6. In the past, there has been a very minimal risk of dermatitis with standard acupuncture needles.

7. Standard sterile acupuncture needles will be used.

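### The stated 47 per group does not follow from the printed inputs: 80% power needs 42 per group, and 47 gives 85%

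*Combined protocol and SAP*

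**What the plan says.** The sample size appears in two places in the combined protocol and SAP.

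- **Section 5(c), Number of Subjects.** The target is set by "we are looking for a difference in narcotic use of 1.5 tablets to be considered significant", with an SD of 2.4 from prior data. The section then says "we will need to study 47 experimental subjects and 47 control subjects to be able to reject the null hypothesis" of equal means, and to "discern a difference of 1.5, with probability (power) 0.8". The Type I error is 0.05. Recruitment is set slightly higher: "A total of 100 patients will be recruited and there will be 50 in the study group and 50 in the control group".
- **Section 5(h), Data Management and Confidentiality.** The prior data are summarised as "the average number of narcotic tablets consumed at 24 hours is 3, with a standard deviation of 2.4". The target is "Overall we are aiming to achieve a decrease of 50% (or 1.5 tablets) for post-operative narcotic use at 24 hours". The section concludes: "The number of patients required for such a difference is 47 experimental subjects and 47 control subjects". It repeats the error rate of 0.05 but not the power. The planned analysis is "The analysis of pain medication use and admission rate will be performed using student t-tests and regression analyses".

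Neither section says whether the test is one- or two-sided. Neither mentions an allowance for loss to follow-up, an inflation for a rank test, or a reduced alpha.

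**The concern.** Section 5(c) prints everything needed to repeat the calculation except the sidedness, so a reader should be able to recover the 47. The standardised difference is 1.5/2.4 = 0.625, and a standard two-sample calculation at 80% power gives a number in the low forties.

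This is the only justification offered for the size of the trial. As printed, a reader cannot tell whether the design power is 80% or 85%, or whether the difference actually used was 1.5 tablets or something smaller. Anyone reporting the trial would carry the statement forward, and nobody could reproduce it. The number of patients recruited, the primary outcome and the analysis are not at stake.

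**Working it through.** **Inputs**

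| Input | Value | Source |
|---|---|---|
| Difference | 1.5 tablets at 24 hours | 5(c), 5(h) |
| SD | 2.4 | 5(c), 5(h) |
| Alpha | 0.05 | 5(c), 5(h) |
| Power | 0.80 | 5(c) |
| Allocation | 1:1 | 5(c) |
| Test | Student t-test | 5(h) |
| Sidedness | two-sided (assumed; the null in 5(c) is equality of means) | not stated |

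**Step 1: try to reproduce 47.** By the normal approximation,

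n per group = 2 × (z₀.₉₇₅ + z₀.₈₀)² × (SD/difference)² = 2 × (1.960 + 0.842)² × (2.4/1.5)² = 2 × 7.849 × 2.56 = 40.19, so 41.

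The t-test calculation (noncentral t) gives 41.17, so 42. Power is 0.798 at 41 per group and 0.808 at 42. The stated 47 is therefore not reproduced; it is 5 per group (10 in total) too high.

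**Step 2: read it the other way.** Power of the two-sided t-test on the same inputs:

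| n per group | Power |
|---|---|
| 42 | 0.808 |
| 47 | 0.850 |
| 50 | 0.872 |

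The requirement for 85% power is 46.95, which rounds up to 47. The difference that 47 per group detects with 80% power at SD 2.4 is 1.40 tablets.

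**Step 3: does the unstated sidedness explain it?** No. One-sided at 0.05 needs 32.35, so 33 per group, which widens the gap.

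**Step 4: does rounding of the inputs explain it?** All figures are for the two-sided t-test at 80% power.

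| Difference | SD | n per group |
|---|---|---|
| 1.5 | 2.45 (upper rounding limit) | 42.86, so 43 |
| 1.45 (lower rounding limit) | 2.449 | 45.76, so 46 |
| 1.41 (half of a mean of 2.82) | 2.4 | 46.46, so 47 |
| 1.25 (half of a mean of 2.5) | 2.4 | 58.84, so 59 |
| 1.75 (half of a mean of 3.5) | 2.4 | 30.52, so 31 |

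Rounding of the printed 1.5 and 2.4, even both at their limits, does not reach 47. Rounding of the mean could: 5(h) prints it as the whole number 3, and any mean from 2.5 to 3.5 would print that way. But half of 2.82 is 1.41, which does not print as 1.5, and both sections print 1.5.

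**The case against.** The strongest reply is that several ordinary planning steps lead to 47 or very near it, so an unreported step is as likely as a wrong figure.

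- **A 10% loss allowance:** 42/(1 − 0.10) = 46.7, so 47.
- **A reduced alpha for the interim look.** Section 5(i) plans analyses after 50 and 100 patients, with termination for a significant difference. If each look used a nominal 0.0294 (an assumption; the documents give no such value), 80% power would need 46.7, so 47, by the normal approximation, or 47.9, so 48, by the t-test.
- **Unrounded prior data.** A mean of 2.86 (difference 1.43) with SD 2.44 gives 46.68, so 47.

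None of these is in the documents. The first is stated nowhere, and 5(c) presents 47 as the number the test itself needs. The second contradicts the printed 0.05, and the third contradicts the printed 1.5. They stand as candidates for the sponsor to check, and as a reason not to assert that 85% power was the intention.

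A second reply is that the interim look undermines the claim that the mismatch is on the safe side. With 0.0294 at the final test alone, power would be about 0.79 at 47 per group and 0.82 at 50. That leaves out the chance of rejecting at the first look. Counting both looks, overall power at 50 per group is about 0.83 to 0.84, still above 0.80. What stands is that the 87% describes a single final analysis at 0.05 and must be labelled so. The lack of a stated alpha adjustment for the interim look is a separate matter.

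It is also fair to say that the practical consequence is close to nil, because 50 per group exceeds both 42 and 47.

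**Conclusion.** The point holds as a minor reporting error. On the printed inputs and a two-sided t-test, 80% power needs 42 per group, not 47; equivalently, 47 per group has 85% power, not 80%. The printed size and power cannot both be right for the printed difference, SD and alpha.

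Confidence is high about the mismatch. It does not extend to which figure is wrong: the size, the power, the difference, the SD, or an allowance left out of the text. The 42 and 85% rest on the two-sided assumption; the one-sided reading makes the discrepancy larger in the same direction. On the printed inputs the error is conservative, since power exceeds 0.80 at both 47 and 50 per group.

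**What to change.** Keep 50 per group. Retrieve the original calculation and restate sections 5(c) and 5(h) so that size and power agree, using whichever of these matches it:

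- 42 per group are needed for 80% power (two-sided t-test, alpha 0.05, SD 2.4, difference 1.5); or
- 47 per group are needed for 85% power, on the same inputs.

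If a different difference or SD, a loss allowance or a reduced alpha was actually used, state that step instead. On the printed inputs, the text may add that 50 per group gives 87% power for a single final analysis at 0.05. Because 5(i) plans a look after 50 patients, that qualifier must stay with the figure. State the sidedness in both places, and print the prior-data mean to at least one decimal so that the 50% reduction can be checked.

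The cost is one sentence in two sections, after looking up the calculation. Enrolment, outcome and analysis are unchanged.

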[name], [name], and [name] are all high volume surgeons in gynecology. Between the three of them, over 500 laparoscopic gynecological procedures are performed per year, providing an adequately sized pool of subjects to meet the recruitment goals. Using anecdotal evidence from past studies performed by [name] it is estimated that 85% of patients will choose to participate. [name], an Assistant Professor at Mount Sinai and Licensed Acupuncturist, will be available to perform intra-operative acupuncture for the first two gynecological cases three days a week. Given this participation rate and the availability of [name], the study is expected to be completed in 6 months.

High volume surgeons in the Gynecology department and the co-investigators who are fellows and residents in the Department of Obstetrics and Gynecology at the Mount Sinai School of Medicine will carry out the study. Nursing staff involved in post-operative patient care will be informed of the study protocol and a copy of the protocol will be readily available for reference in the hospital.

[name], [name], and [name] offices' will be utilized for presurgery registration and consent of participants. Participating attending and fellows will obtain consent. [name] will be responsible for preparing and placing the acupuncture needles in the OR. This will be done immediately after the induction of anesthesia and proper positioning of patients. The needles will be placed in the hands and feet, area's that can be accessed after the patient is appropriately prepped and draped. The needles will be in-situ for approximately 15 minutes, which is the average time acupuncture needles are used for a treatment.

Post operative data collection will be performed by OR nursing staff and Drs. [name], [name], [name], [name], and [name]. Data analysis will be performed in the office of the OB-GYN Department by the co-investigators with consultation of the hospital statisticians as needed.

5) Study Design

a) Recruitment Methods

Eligible participants for the study are patients of [name], [name], or [name] who are planning to have laparoscopic gynecological procedure. Potential study participants will be provided information about the present study during their pre-operative visit, which occurs 1-3 weeks prior to their surgery. No additional advertisements will be utilized for patient recruitment.

b) Inclusion and Exclusion Criteria

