The purpose of the present study is to determine the effectiveness of acupuncture in post-operative pain management in laparoscopic gynecological procedures. The endpoints of this study are narcotic use at 24 hours, hospital admission for pain management, and narcotic use for 7 days following surgery. Primary outcome measures narcotic use at 24 hours. Secondary outcome measures are quantity of opioids used for pain management for the first 7 days post operatively and hospital admission.

Safety endpoints that would cause a subject’s participation to end are contact dermatitis from the placement of acupuncture needles. This is a very uncommon response.

f) Procedures Involved in the Human Research

Female subjects who are scheduled to undergo a laparoscopic surgery of the uterus, adnexa or ovaries for benign disease. All procedures will be performed for clinical patient care and not solely for research purposes. Patients will be offered enrollment in the study during their pre-operative visit with [name], [name], and [name] and consented by one of the participating fellows.

Once consented, participants will be randomized into the acupuncture (study) or sham acupuncture (control) group using a computer-generated randomization system. The patient will be blinded to the group to which they are assigned.

After general anesthesia induction and proper positioning of the patient, but prior to surgical incision, the acupuncture needles will be placed. In the study group, the proposed acupuncture points are LR-3, GB-41, GB-34, TH-5, MH-6, which are all found on upper and lower extremities. Standard

	Protocol Name:	The Role of Acupuncture in Post-Operative Pain Management in Gynecological Patients
	Principal Investigator:	[name]
	Primary Contact Name/Contact Info:	[name], [name]
	Date Revised:	6/19/2016
	Study Number:	1896888

acupuncture needles 29 and 30 gauge will be used throughout. As in standard acupuncture treatments, the needles will be left in-situ for a total of 15 minutes. In the control group, the primary surgeon (who has no acupuncture experience) will quickly place 5 needles in random spots on the patients' hands and feet. The needles will be immediately removed. Anesthesiologists will be informed to not make any alterations in their typical anesthesia regimen based due to the placement of acupuncture needles.

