Potential study subjects will be informed and consent obtained in the outpatient setting during their pre-operative visit. The potential subjects will have adequate time to review the material, free of time constraint or a sense of obligation or coercion. Consent will be obtained by Drs. [name], [name] or [name] or by one of the fellows during their pre-operative visit in their private office, not immediately pre-operatively. The consent process will take place in a private room, not in a public area, such as a waiting room or public holding area. Prior studies have shown the average time to appropriately consent a patient during a pre-operative visit is 10 minutes. We will allocate at least 10 minutes to each individual consent process, however more time will be available if needed to address all patient questions and concerns. Patients will be given a copy of the study template and consent document, which will be available in English.

Children

 Mount Sinai	Protocol Name:	The Role of Acupuncture in Post-Operative Pain Management in Gynecological Patients
	Principal Investigator:	[name]
	Primary Contact Name/Contact Info:	[name], [name]
	Date Revised:	6/19/2016
	Study Number:	1896888

No children will be included in this study. Women must be over the age of 18 to consent.

Cognitively Impaired Adults

No cognitively impaired adults will be included in this study. Each participant must have the cognitive ability to consent herself.

Non-English Speaking Subjects

English speaking patients will be included. Women that speak any other language will not be included in our study

Waiver or Alteration of the Consent Process

There will not be a waiver or alteration in the consent process.

13) Process to Document Consent in Writing

The consent of all subject will be documented in writing, using the standard PPHS consent template.

14) Vulnerable Populations

Indicate specifically whether you will include (target) or exclude each of the following populations:

Include	Exclude	Vulnerable Population Type
	X	Adults unable to consent
	X	Individuals who are not yet adults (e.g. infants, children, teenagers)
	X	Wards of the State (e.g. foster children)
	X	Pregnant women
	X	Prisoners

15) Multi-Site Human Research (Coordinating Center)

N/A

16) Community-Based Participatory Research

N/A

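### As written, women are randomized weeks before surgery with no concealment stated, so pre-surgery losses follow randomization and the arm could influence scheduling

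*Combined protocol and SAP*

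**What the plan says.** **Sequence.** The opening summary and section 5(f) both place randomization directly after consent; section 5(f) reads "Once consented, participants will be randomized into the acupuncture (study) or sham acupuncture (control) group using a computer-generated randomization system". Section 12 has consent obtained "during their pre-operative visit in their private office, not immediately pre-operatively". Section 5(d) describes that visit as "typically occurring 1-3 weeks prior to surgery", and sections 3 and 5(a) give the same interval. Section 5(f) has the needles placed after induction and positioning and before incision.

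**Who needles, and when they are available.** Section 4 has the licensed acupuncturist available to "perform intra-operative acupuncture for the first two gynecological cases three days a week". For the control group, section 5(f) says "the primary surgeon (who has no acupuncture experience) will quickly place 5 needles".

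**Related provisions.** The summary describes participants as already scheduled for surgery. The summary and section 5(f) blind the patient to her group and mention no other blinding. Section 5(j) applies intention to treat to subjects who choose to withdraw, using the data collected until then. The document does not say when the allocation is revealed, to whom, or how it is concealed. It also does not say how a randomized woman is counted if her operation is cancelled or changed.

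**The concern.** Two consequences follow from the sequence as written.

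First, any cancellation, postponement or change of operation between the office visit and surgery comes after randomization. A woman who is never operated on has no 24-hour narcotic count, so she cannot contribute to the primary endpoint whatever the analysis is called.

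Second, the arms need different resources. A woman allocated to acupuncture but listed third, or on an uncovered day, must be moved or go without the assigned needling. A sham patient in the same place needs neither, because her surgeon does the needling. If the arm is known before the list is final, it can influence who is moved or postponed. This requires no misconduct, only an attempt to deliver the assigned treatment.

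What is at stake is comparability in time of day, day of week and the mix of cases that stay on the list. Section 5(f) has discharge or admission decided after four hours, and admission is a secondary endpoint, so start time could plausibly matter there. The demographic items listed in section 5(h) are subject code, age, operation and study group. Slot and start time are not among them, so the planned regressions could not readily adjust for an imbalance.

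**Working it through.** **1. The written sequence.**

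| Step | When | Source |
|---|---|---|
| Consent | Office visit, 1-3 weeks before surgery | Sections 5(a), 5(d), 12 |
| Randomization | Once consented; no other trigger given | Summary, section 5(f) |
| Needling | After induction, before incision | Section 5(f) |

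Nothing between the second and third steps requires the allocation, apart from getting the acupuncturist to the right cases.

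**2. Does pre-surgery loss threaten power?** The inputs are a difference of 1.5 tablets (section 5(h): "Overall we are aiming to achieve a decrease of 50% (or 1.5 tablets) for post-operative narcotic use at 24 hours"), SD 2.4, power 0.80 (section 5(c): "discern a difference of 1.5, with probability (power) 0.8") and alpha 0.05 ("The Type I error probability associated with this test of this null hypothesis is 0.05"). Sidedness is not stated; I take two-sided.

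The plan's own figure is 47 per arm. The normal formula gives n = 2(1.96 + 0.8416)² × 2.4² / 1.5² = 40.2, so 41. The exact t-test gives 41.2, so 42. The 47 is not reproduced, but it errs on the large side and does not affect this point.

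The plan recruits 50 per arm, which is 3 (6%) above the stated 47 and 8 (16%) above the recomputed 42. The documents give no loss rate, so the rates below are assumptions.

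| Loss after randomization | Left per arm | Power (two-sample t-test) |
|---|---|---|
| 0% | 50 | 0.87 |
| 6% | 47 | 0.85 |
| 10% | 45 | 0.83 |
| 16% | 42 | 0.81 |
| 20% | 40 | 0.79 |

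Power falls below 0.80 only at 41 or fewer per arm, a loss of 9/50 = 18%.

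**3. Is there room for the arms to differ in slot?** Covered slots number 2 × 3 = 6 a week, or 6 × 26 = 156 in the six months that section 4 expects. The three surgeons perform over 500 procedures a year, so at least 250 in six months. Even if every covered slot were one of their cases, at most 156/250 = 62% of their procedures would be covered. A substantial share therefore falls outside, where only sham could be delivered.

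**4. Could both arms be drawn from covered slots?** At the 85% participation that section 4 assumes, 156 × 0.85 = 133 women in 26 weeks, against 100 needed. Recruitment stays within six months if at least 100/132.6 = 75% of covered cases are eligible.

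**5. Can the bias be sized?** Not from the documents. Take SE = 2.4 × √(2/50) = 0.48 tablets. A spurious difference b changes the chance of a false positive favouring acupuncture from 0.025 to 1 − Φ(1.96 − b/0.48), where b is the share of sham cases out of slot times the extra tablets such cases use. All inputs here are assumed.

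| Sham cases out of slot | Extra tablets in those cases | b | False-positive chance |
|---|---|---|---|
| 50% | 0.5 | 0.25 | 0.075 |
| 25% | 0.25 | 0.0625 | 0.034 |
| 10% | 0.5 | 0.05 | 0.032 |
| 50% | −0.5 | −0.25 | 0.007 |

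Even the direction depends on what is assumed.

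**The case against.** The strongest reply is that the text gives an order, not a date. Randomizing once consented is compatible with a draw on the day of surgery, and section 12's exclusion of the immediate pre-operative period concerns consent only. That stands: the exact moment is not stated. But no later trigger is written, and staff who followed the text literally would draw early.

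Second, operations are already scheduled at consent, and no passage describes rebooking by arm. Section 4 bases the completion time of the whole study on the participation rate and the acupuncturist's availability, which fits both arms being drawn from covered slots. This also stands, and it narrows the route to changes of case order or date made by staff. It does not close that route, because nothing confines sham cases to the same slots.

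Third, patients are blinded, so their own cancellations cannot respond to the arm. Loss unrelated to arm costs some precision and does not bias the comparison. This is correct.

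A reader might infer three stronger things that the documents do not support:

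- **That sham cases will fall anywhere on the list.** The text is silent on this.
- **That losing more than 3 per arm leaves the trial underpowered.** At an assumed 10% loss the chance that both arms keep 47 is only 0.06, but 47 exceeds what the stated inputs need. The chance that both keep 42 is 0.89.
- **That the false-positive rate triples.** The 0.075 is one choice of assumed inputs; others give 0.007 to 0.034.

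Nor does any passage say that the consenting surgeons and fellows see allocations before surgery. Surgeons do learn the arm when they place sham needles, and the proposed fix does not change that.

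**Conclusion.** The point holds as a design weakness in the written sequence. Consent comes 1-3 weeks before surgery, randomization follows it, no concealment or later draw is stated, and only one arm depends on limited slots. Followed as written, the plan would leave randomized women without a primary outcome if their surgery does not go ahead, and would let the allocation influence case order or rescheduling.

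The size of any bias cannot be given. It depends on how often staff would move cases by arm and on whether slot affects narcotic use or admission, and the documents give figures for neither. The effect on power is small: 0.83 at 45 per arm and 0.81 at 42, assuming a two-sided test and the stated 1.5 and 2.4. The change is worth making before enrolment because an imbalance in slot could not readily be repaired afterwards, and because the remedy is cheap.

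**What to change.** In the summary and section 5(f), replace the sentence on randomization with text to this effect:

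- Only women already booked in a slot that the acupuncturist covers are enrolled, in both arms, and the case order is fixed before allocation.
- The allocation is concealed (sealed opaque envelope or system call) and drawn in the operating room after induction and positioning, just before needling. A woman whose operation is cancelled or moved out of a covered slot before the draw is not randomized.
- All women randomized at that point are analysed in their assigned group.

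Recording slot and start time on the data sheet would let the balance be checked.

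**Cost.** A few sentences and a day-of-surgery allocation step. The acupuncturist attends some cases that turn out to be sham, although section 4 already has that person available for those slots. The pool is limited to at most 6 cases a week. The 133 women in 26 weeks is a best case: it precedes exclusions and assumes that every covered slot is a laparoscopic case of a participating surgeon. If fewer than about 75% of covered cases are eligible, recruitment would run past six months.
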